**Table 3. Sample Collection Intervals**

		Week 1/Day 0, Infusion Day		Week ^																		
	Screening	Pre-infusion	Post-infusion	1	2	2*	3	4	5	6	7	8	9	10	11	12	13	14	15	16	24	
SCD Pre-Transplantation	X	X	X	X	X	X	X	X	X	X	X	X	X	X	X	X	X	X	X	X	X	
SCD Post-Transplantation	X	X	X		X		X	X		X		X		X		X		X		X		X
HbAS	X	X	X		X		X	X		X		X		X		X		X		X		X
HbAA	X	X	X		X		X	X		X		X		X		X		X		X		X
Approximate Volume of Blood (mL)	50	100	5	10 (per sample collected)																		

^All patients will follow the sample interval until the percentage of biotinylated RBCs has decreased to the lower limit of detection (approximately <0.06%), at which time the next interval for that patient will be the final 6 month (week 24) interval.

2\* = Bi-week 2

**6.10 Antibody Detection:** To test for antibodies to biotinylated RBCs, plasma samples will be tested using gel card antibody detection(MTS anti-IgG Card, MTS084024, Ortho Clinical Diagnostics) as previously described (11). The detection of specific antibodies to bioRBC does not determine whether these antibodies are physiologically active or are clinically significant. Thus far, all identified pre-existing, naturally occurring anti-bioRBC antibodies are neutralized by biotin compounds, while induced anti-bioRBC antibodies are expected to be inhibited by bioRBC and not by free biotin as previously published (11). It is speculated that this is analogous to penicillin-type drug-dependent antibodies with biotin covalently attached to RBC surface proteins acting as immunogenicity enhancing haptens. In those reported cases of anti-bioRBC antibody detection, biotinylation occurred at higher concentrations (54-162 µg/mL), antibodies were transient and no longer detected after 6 months, and did not alter the red cell survival (4,11).

## 7.0 Analysis of the Study

**7.1 Flow Cytometry Analysis:** Enumeration of BioRBCs will be performed by flow cytometry. Samples will be collected pre and post biotinylation prior to infusion (as per section 6.6), at 20 minutes post infusion (time zero), and as described in section 6.9 & Figure 1. To isolate the RBC fraction, 40 µL of whole blood aliquoted in triplicate will be mixed with 1 mL of wash buffer, centrifuged at 10,000 x g until the rpm value is reached, and supernatant will be discarded (repeat x1). The final washed RBC pellet will be resuspended in 80 µL of wash buffer, mixed with 20 µL of a 1:20 dilution (in PBS) of streptavidin-phycoerythrin (SA-PE; S-866; Molecular Probes, Eugene, OR), and incubated for 30 min at room temperature in the dark. The staining reaction is stopped by adding 3 mL of wash buffer, centrifuging at 1500 rpm for 5 minutes, and removing the aspirate. RBCs will then be suspended in 500 µL of wash buffer, and will be filtered through a 0.45 µm filter prior to flow cytometry (FACSCalibur, BD Biosciences, San Jose, CA). Percentages of BioRBCs will then be measured by flow cytometry.

**7.2 F-cell and S-cell measurement:** Simultaneously with the measurement of BioRBCs by flow cytometry (see section 7.1), samples will be analyzed with an additional color (3-color flow cytometry) for Biotin, HbF, and HbS. After incubation with SA-PE and two washes, the cells will be mixed with a 2 µL/mL solution of glutaraldehyde/PBS. Cells will be gently mixed and incubated at room temperature for 10 minutes. Cells will be centrifuged at 2500 rpm x 5 min, then incubated at room temperature with 1mL 0.1% Triton X solution for 10 minutes. After centrifugation at 2500 rpm x 5 minutes, cells will be stained for 30 minutes at room temperature with a fluorescein isothiocyanate (FITC)-conjugated monoclonal antibody to HbS and allophycocyanin (APC)-conjugated monoclonal antibody to HbF prior to analysis by flow

cytometry. The F per F cell can be calculated from the percent F cells, the percent HbF (determined by HPLC, see section 7.3), and the MCH.

7.3 **Hb Content:** BioRBCs will be isolated from post-infusion blood samples using streptavidin-coated magnetic beads or flow cytometry separation. The collected BioRBCs and the negative fraction will be analyzed by high performance liquid chromatography (HPLC) for hemoglobin content.

7.4 **Measurements of delay time for sickling of individual red cells:** Blood from patients will be diluted 1500 to 3000-fold, depending on the hematocrit, into PBS. 10  $\mu$ L of the cell suspension is added to the wells of a 384-well plate. The well plate is inserted into a humidified chamber of a Biotek “Lionheart FX Automated Microscope System” and, for patients with SS disease, deoxygenated with a mixture of 96% nitrogen and 4% oxygen to induce sickling. Everything that follows is fully automated. Images taken in 430 nm light (the absorption peak of deoxyhemoglobin) of 100-200 cells settled on the bottom of each of the 384 wells are measured every 15 minutes for up to 8 hours (see Figure 2). A single scan of all 384 wells takes 15 minutes because the autofocusing system of the instrument requires about 2.3 seconds to obtain a focused image from each well and 56 seconds to scan a row of 24 wells. Because images are taken of 40,000 to 80,000 cells, excellent statistics can be obtained on more than 20 different blood samples in a single experiment (using less than about 100 nanoliters from each patient). Sickling times are determined with our in-house developed, robust image analysis software (12), which compares several metrics of the cell image to determine in which 15 minute interval the cell has become distorted, i.e. sickled. These include the eccentricity (deviation from a circular projection) and ratio of the optical density at the periphery of the cell to that at the cell center (unsickled cell is more transparent in the center). From the fraction sickle vs time (Figure 3), the final output for each blood sample is a t50 for sickling. The comparison between SS and AS cells shows the enormous sensitivity to the intracellular hemoglobin composition (> 90% Hb S in SS cells; 60/40 HbA/Hb S mixture in AS cells).

[figure not shown]

Figure 2. Images of cells at 135 and 150 minutes after the start of deoxygenation with 96% nitrogen and 4% oxygen. Cells that sickle between 135 and 150 minutes are circled. At 150 minutes 37 % of the 84 cells are sickled.

[figure not shown]

Figure 3. Mean fraction sickled as a function of time following deoxygenation of SS and AS cells with 96% nitrogen and 4% oxygen. The error bars correspond to one standard deviation from the mean of the fraction sickled in 96 wells. They are about twice the expected value due to the finite number (~100) of cells in each well. The higher standard deviations compared to AS is mainly caused by small differences in the geometry of each of the 10 microliter droplets, which result in differences in the fraction sickled at the same deoxygenation time due to differences in the rate of oxygen diffusion out of the droplet. The fraction sickled vs deoxygenation time for the SS cells is very similar to the kinetics for AS cells when deoxygenated with 100% nitrogen.

7.5 Other Analysis: A portion of collected RBCs will be used for imaging flow cytometry, HbF staining, HbS single cell Western Blot, and assay development. Duplicate samples of approximately 2 mL (range 1-5 mL) of pre-infusion, time zero, and subsequent patient samples will be sent to our collaborators at bluebird bio Inc, for parallel analysis and assay development. No samples will be sent to our collaborators until a Material Transfer Agreement (MTA) has been established.

Another portion of collected RBCs will be used for measurement of glycolytic metabolites. Duplicated coded samples of approximately 450  $\mu$ L will be sent to our collaborators at Agios Pharmaceuticals, Inc. for parallel analysis. The results of these findings will be reidentified at the NIH to answer this new analysis. An MTA for this collaboration has been fully executed.

7.6 Data and Statistical Analysis: This is an exploratory study designed to test methodology and assay development for the purposes of studying red cell survival in patients with SCD. RBC survival curves will be generated for each participant. Mean potential RBC life span (MPL) will be determined by plotting the percentage of remaining biotinylated RBCs in circulation against time after transfusion. Median RBC survival and mean RBC age will be calculated from these curves. Correlation of mean RBC survival with known markers of red cell survival will be performed using Pearson Correlation. The mean of each participant's clinical laboratory values during the study period will be used for correlation with RBC survival. Average MPL among the groups studied will be examined descriptively using means and standard deviations. The differences between groups will be used to examine the feasibility and guide the design of larger, definitive studies; in this pilot study, statistically significant differences are not generally anticipated. Similarly, information regarding hydroxyurea use,  $\alpha$  globin genotype, etc are likely to not be powered to see an effect.

7.7 Mathematical Model: We assume that in erythropoietic homeostasis, RBC lifetime is proportional to the inverse of the reticulocyte fraction such that RBC survival is lowest in patients with the highest reticulocyte counts. We will subsequently develop a mathematical model to predict the percentage of necessary hemoglobin to reverse SCD from reticulocyte count and RBC half-life.

7.8 **Off Study Criteria:** Patients reserve the right to come off study for any reason during the study period. Patients may be taken off-study by the PI if there is a health-related event during the course of the study that affects RBCs lifespan or production of RBCs including hemorrhage or need for transfusion. In the event of pregnancy after infusion of biotinylated RBCs, the patient will remain on study unless directed otherwise by the patient.

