## PROTOCOL SUMMARY

### Synopsis

Title:	Red Cell Half Life Determination in Patients with and without Sickle Cell Disease
Study Description:	
This study will use biotin-labeling of red blood cells (RBCs) to determine the mean potential lifespan (MPL) of RBCs in patients with sickle cell disease (SCD) compared to patients who have successfully undergone curative bone marrow transplantation (BMT, allogeneic or autologous), participants with sickle cell trait, and healthy donors without SCD. Previous studies have corroborated the MPL of healthy donor RBCs to be approximately 115 days while RBCs from patients with SCD have a much more variable but consistently shorter MPL of approximately 32 days. Allogeneic BMT is a curative therapy for the treatment of severe SCD with stable, mixed donor-recipient chimerism after BMT sufficient to reverse the sickle cell phenotype by virtue of improved donor red cell survival compared to the ineffective erythropoiesis of SCD. We predict that the hematologic variables associated with red cell survival among patients with SCD vs. participants with SCT and healthy donors can be used to determine the necessary amount of corrected hemoglobin required to overcome the red cell pathology of SCD. Data generated will be used to determine the utility of performing a population study of RBC lifespan in gene therapy treated patients to ultimately target the percentage of transferred globin gene needed to reverse SCD. The data generated will refine our understanding of the degree of correction necessary to reverse the phenotype of SCD.

Objectives:	
Primary Objective: To determine and compare red blood cell survival in patients with SCD, patients with SCD who have undergone BMT, participants with SCT, and healthy donors, and validate the association of red cell survival with known markers of increased red cell survival.
 
Exploratory Objective: To create a mathematical model incorporating RBC survival and reticulocyte count to determine the necessary amount of normal hemoglobin, and therefore vector copy number or amount of transferred globin, required for gene therapy protocols.

Endpoints:	
Primary Endpoint: Red blood cell survival
 
Secondary Endpoints: Relationship of red blood cell survival to hematologic parameters. Antibody detection to biotin.

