- 6.4 **Pre-Biotinylation Washing:** The whole blood product will be visually inspected carefully; if clots/clumps are observed, product will be filtered before further processing. Blood will be centrifuged at 1000 x g (2142 rpm), deceleration (DEC) 4 at room temperature (RT; 17°C –25°C) for 10 minutes in table top centrifuge. The plasma layer will be aspirated and saved for use in reconstituting RBCs after biotin labeling. RBCs will be washed three times with 4 vol (4:1 wash:

RBCs) of PlasmaLyte A (Baxter healthcare Corp, Deerfield, IL). Washed RBCs will be resuspended in sufficient wash buffer to yield a 25% suspension of RBCs.

6.5 **Preparation of Biotin:** The CC-TAG-Biotin (ChemConnection BV, Netherlands) is stored in a -20°C freezer and should be allowed to come to room temperature (~10-15min) before opening of the vial to avoid saturation of the biotin reagent. To prevent hydrolysis of the biotin reagent before addition to the RBCs, the biotinylation reagent will be prepared in wash buffer before use (within 20 minutes). A solution containing 1 mg/ml biotin will be prepared by dissolving 1 mg biotin in 1 mL PlasmaLyte A. This solution will then be sterilized by filtration through a 0.22- $\mu$ m syringe filter (21062-25; Corning Glassware, Corning, NY).

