6.6 **Biotinylation Reaction:** Biotinylation will be performed under a sterile Class 2 laminar flow hood in DTM. The appropriate volume of biotin solution will be added with gentle agitation to the 25% RBC suspension to give the desired final concentration of biotin of 18  $\mu$ g/mL, incubated at room temperature for 30 minutes (Preclinical data shows efficiency of biotinylation of sickle RBCs from 1-80  $\mu$ g/mL, however RBC morphology becomes deformed at concentrations >54  $\mu$ g/mL. Flow cytometry peaks separating biotin labeled RBCs from unstained control is best at 18  $\mu$ g/mL compared to lower biotin concentrations, without any evidence of RBC morphology changes at 18  $\mu$ g/mL). The reaction will be terminated by sedimentation of RBCs at 1000 g (2142 rpm), deceleration (DEC) 4 at RT for 10 minutes followed by three 4:1 (vol/vol) buffer washes with PlasmaLyte A, sedimentation, and resuspension; this removes the remaining biotinylation reagent as well as any reaction and hydrolysis byproducts. The washed BioRBCs will be passed through an 18um filter (Hemo-Nate Syringe Filter, Utah Medical Products, Inc, Midvale, UT) and resuspended in autologous plasma at a hematocrit (Hct) of 50% (range 40-60%). 150  $\mu$ L (range 50-500  $\mu$ L) of pre-biotinylated RBCs and 150  $\mu$ L of post-biotinylated RBCs will be withheld and sent to the [name] laboratory for pre-clinical studies (to ensure all cells are labeled and that there is a baseline separation of labeled and unlabeled cells on flow cytometric histogram) via methodology described below (see section 7.1).

6.7 **Final Product:** Final samples are removed for CBC, biotin labelling efficiency determination via flow cytometry, and safety assays (sterility and endotoxin). Release of the drug product is contingent on meeting the criteria listed in the table below (Table 1), which are also listed in the Certificate of Analysis in Module 3.2.P.5.4. For Safety testing, the final drug product must have an endotoxin level of  $\leq$  5 EU/mL and be negative for contamination in the sterility tests. Since the product is infused fresh, release for use is based on gram stain for sterility, with post-infusion testing based on a 14 day culture. The percent hematocrit and the percent of biotinylated RBC's will serve as a measure of purity and identity of the product.

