## 8.0 Drug Formulation, Availability, and Preparation

- **Biotin**

CC TAG BIOTIN ® (Biotin 3 sulfo N Hydroxysuccinimide ester sodium salt) is derived from the natural form of biotin, which is the D enantiomer (Vitamin B7 or B8 according to nomenclature of each country). Because of its small molecular size CC TAG Biotin (small spacer arm: 13.5 Å, between the biotin and the sulfo NHS group) can be conjugated to many proteins without altering their biological activities.

Sulfo NHS activated biotin reacts efficiently with primary amino groups (-NH2) in pH 7-9 buffers to form stable and covalent amide bonds. Proteins from plasma membrane cells generally have several primary amines in the side chain of lysine (K) residues that are available as targets for attachment of biotin. Biotin binds with high affinity to avidin and streptavidin proteins. Therefore the tracking of biotin labelled cells with the CC TAG BIOTIN ® can be performed easily by flow cytometry with fluorescent streptavidin. Biotin labelled proteins can also be easily detected in ELISA, dot blot or Western blot applications using streptavidin or avidin conjugated probes.

The new cGMP CC-TAG-BIOTIN® has been demonstrated to be efficient in labeling blood cells (RBC, WBC and platelets) *ex vivo*. It will reduce the safety concerns and contribute to overcome the need for non- radioactive methods within the framework of *in vivo* studies in humans.

Supply: ChemConnection. (commercially available)

Preparation: As per section 6.5, CC-TAG-Biotin is stored in a -20°C freezer and should be allowed to come to room temperature (~10-15min) before opening of the vial to avoid saturation of the biotin reagent. To prevent hydrolysis of the biotin reagent before addition to the RBCs, the biotinylation reagent will be prepared in wash buffer before use (within 20 minutes). A solution containing 1 mg/ml biotin will be prepared by dissolving 1 mg biotin in 1 mL PlasmaLyte A. This solution will then be sterilized by filtration through a 0.22-µm syringe filter (21062-25; Corning Glassware, Corning, NY).

Storage: CC-TAG-Biotin is moisture-sensitive. Store reagent at -20°C in the original container with desiccant. To avoid moisture condensation onto the product, vial must be equilibrated to room temperature before opening.

Route of Administration: As per section 6.6 and 6.8, biotin will be applied *ex vivo* to patient RBCs, then biotinylated RBCs will be reinfused intravenously to the patient.

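### Section 7.1 filters the stained red cell suspension through a 0.45 µm filter before flow cytometry; intact red cells would not pass, so the assay behind the primary endpoint cannot be run as written

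*Combined protocol and SAP*

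**What the plan says.** Section 7.1 washes whole blood aliquots, stains the red cells with streptavidin-phycoerythrin and washes again. The red cells are then taken up in 500 µL of buffer and, the same sentence continues, "will be filtered through a 0.45 µm filter prior to flow cytometry". The next sentence is the measurement itself: "Percentages of BioRBCs will then be measured by flow cytometry". No step recovers cells from the filter, and no other section corrects or explains the 0.45 µm figure.

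The result feeds the main outcome. The Synopsis names "red blood cell survival" as the primary endpoint, and section 7.6 says that MPL is "determined by plotting the percentage of remaining biotinylated RBCs in circulation against time after transfusion".

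The protocol specifies a pore size in two other settings:

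- Section 6.6, for cells that must come through: "The washed BioRBCs will be passed through an 18um filter".
- Sections 6.5 and 8.0, for the biotin reagent, which contains no cells: "This solution will then be sterilized by filtration through a 0.22-µm syringe filter".

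**The concern.** A filter placed before a cytometer should remove clumps and let single cells through. A 0.45 µm pore is of the order the protocol itself uses to sterilise a fluid (0.22 µm), and far below the 18 µm it uses when red cells must pass. Read literally, section 7.1 holds back the cells that the assay is meant to count.

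At stake is whether the stated method can yield the BioRBC percentage at all. Section 7.6 names no other route to MPL. The same assay is cited in section 6.6 for the pre-infusion labelling check, and the percentage decides when sampling stops (about 0.06%, section 6.9 and Table 3). Section 7.6 describes the study as a test of methodology and assay development that is to guide larger studies, so someone is likely to follow the written assay later.

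**Working it through.** The plan gives no figure to reproduce here. The check compares pore size with cell size.

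**Inputs from the documents**

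- Pore in the assay: 0.45 µm (section 7.1).
- Filter that BioRBCs pass: 18 µm (section 6.6).
- Filter for the cell-free biotin solution: 0.22 µm (sections 6.5 and 8.0).

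**Assumed inputs (the documents give no red cell dimensions)**

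- Resting diameter 6-8 µm.
- Volume V of 60-120 fL (1 fL = 1 µm³).
- Membrane area A of 100-160 µm².

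**Step 1. Resting cell against pore.** 6 / 0.45 = 13.3 and 8 / 0.45 = 17.8. The cell is 13 to 18 times as wide as the pore. For the section 6.6 filter, 18 / 8 = 2.25 and 18 / 6 = 3.0, so there the pore is wider than the cell.

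**Step 2. Deformed cell against pore.** Red cells deform, so resting diameter alone does not settle the matter. The narrowest tube that holds the cell's volume without stretching its membrane is a cylinder of diameter D with rounded ends, found by solving

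V = (D/4)(A − πD²) + πD³/6.

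| V (fL) | A (µm²) | Narrowest D (µm) | D / 0.45 |
|---|---|---|---|
| 60 | 100 | 2.58 | 5.7 |
| 60 | 135 | 1.82 | 4.1 |
| 80 | 120 | 2.87 | 6.4 |
| 90 | 135 | 2.85 | 6.3 |
| 100 | 145 | 2.94 | 6.5 |
| 120 | 160 | 3.22 | 7.2 |

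The narrowest width is about 1.8-3.2 µm, or 4 to 7 times the pore.

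**Step 3. Membrane needed to fit the pore.** With p = 0.45 µm, the cylinder length is L = (V − πp³/6) / (πp²/4) and the area needed is πpL + πp². For V = 60 this is 534 µm², and for V = 120 it is 1,067 µm². The assumed membrane area is only 100-160 µm². Every combination tried gives retention of intact cells.

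**Step 4. What the cytometer must be given.** To count cells at the 0.06% limit with a given coefficient of variation (CV), the events needed are about 1 / (CV² × 0.0006). At an illustrative CV of 10% that is 1 / (0.01 × 0.0006) = about 167,000 red cell events, and at 5% about 667,000. A filtrate without intact cells cannot supply them.

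**The case against.** The best reply is that this is a slip in the text, that the laboratory does something else, and that a failure would be noticed. Much of that stands.

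- Section 6.6 withholds cells before and after biotinylation to confirm labelling and separation of the peaks, by the section 7.1 method. An empty filtrate would probably show up there, before infusion. Table 1 also requires at least 80% biotinylated cells by flow cytometry for release, although it does not say that this test uses the 7.1 preparation.
- Section 6.6 reports preclinical flow results at several biotin concentrations, so labelled red cells have evidently been measured. The filter used for that work is not stated. This makes a wrong figure or unit more likely than an unworkable assay, but it does not validate 0.45 µm.

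Four stronger readings are tempting, and the documents do not support them.

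- *Every survival point is lost or invalid.* The text shows only what would happen if 7.1 were followed literally. Section 7.2 also measures biotin, with a preparation that branches off after staining and two washes and names no filter. Section 7.5 sends duplicate samples for parallel analysis. Neither is named as the source of MPL, but other biotin measurements exist.
- *The percentage would be read on debris, or biased differently in sickle cell disease because those cells are more rigid.* The documents say nothing about passage, staining or gating of fragments. A nearly empty tube is the more obvious result, and no bias in MPL or in the group comparison has been shown.
- *The 40-fold ratio, 18 / 0.45, measures the damage.* It compares filters with different jobs, an infusion product and a cytometer sample. It is not an effect size; the relevant comparison is pore against cell.
- *The filter is meant only for the wash buffer.* The subject of the sentence is the red cells, so the text as it stands does not carry that meaning.

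None of this makes the written step workable.

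**Conclusion.** Wrong as written. Section 7.1 puts the stained red cells through a pore that intact cells cannot pass, so the stated method could not give the BioRBC percentage on which the survival curve and MPL rest. The conclusion depends on red cell dimensions from outside the documents. It is insensitive to them: over the whole assumed range the narrowest deformed cell is still at least 4 times the pore. The protocol's own choice of 18 µm for cells and 0.22 µm for a cell-free fluid points the same way.

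The most likely explanation is an error in the figure or the unit. The intended value cannot be recovered from the documents. The finding concerns the written method: it does not show that laboratory data are invalid, and it changes no sample size, power or error rate.

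**What to change.** 1. In section 7.1, replace 0.45 µm with the pore or mesh size that the laboratory has verified for intact red cells, taken from its working procedure.
2. In section 7.2, state whether the same filtration applies to the three-colour preparation.
3. Confirm the step on the pre- and post-biotinylation samples already withheld under section 6.6. Filtration is the last step before the cytometer, so one stained suspension can be split and read filtered and unfiltered, comparing event count and labelled percentage. A mixture of the two samples in known proportion is the more informative test, because a percentage near 0 or 100 has little room to move.

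The cost is one corrected figure, one added sentence and a short bench check on material already held. No visit, blood volume, sample size or analysis changes.

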There are two methods to determine red cell survival; *in vivo* cohort methodology or *in vitro* population labeling. Cohort labeling involves labeling hemoglobin with oral glycine containing radioactive or stable isotopes ( $^{15}\text{N}$ -glycine) which becomes metabolically incorporated into hemoglobin-synthesizing normoblasts in the bone marrow (BM). The resulting labeled RBCs are similarly aged, and mature and are released from the BM at the same time. The quantification of RBC lifespan would therefore require a full time-course study of approximately 150 days (based on HD data and time to maximum  $^{15}\text{N}$ -glycine detection) and analysis by mass spectrometry. While this method allows study of single age cohort and does not require *ex vivo* manipulation, samples are not analyzed until the completion of the study and would therefore not be available live throughout the study.

In contrast to the cohort method, current population labels include biotin and  $^{51}\text{Cr}$ , which tag a representative population of circulating RBCs irrespective of RBC age. The ideal label has minimal RBC manipulation, stability throughout the life of the RBC, lack of RBC shortening due to labeling, and lack of toxicity to the individual receiving labeled RBCs. Biotinylated RBCs (BioRBCs) confer advantages over radiolabeled methods by upholding these ideals in addition to posing no radiation risks and providing a more acceptable method to study vulnerable populations such as women, fetuses, infants, and children. A further advantage of the population study method is the label (ie. biotin) can be easily tracked via flow cytometry, and the analysis can be complexed with additional characterization parameters such as intracellular staining for different hemoglobin moieties. The labeled population of cells is representative of what is found in circulation at the time of labeling and therefore the RBCs are of different ages. This type of study has allowed for measurement of phosphatidylserine exposure on RBCs as they age *in vivo* (8) and the quantification of lifespan of F cells versus non-F cells in SCD patients as previously described (7).

Additionally, a retrospective analysis of a population study data set suggests that a 28-day window may be sufficient for accurate quantification of MPL(4).

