## 3.0 Scientific and Clinical Justification

The safety of biotinylating RBCs in SCD patients is known as is a shortened RBC survival. Known influencers of RBC survival such as ARC, %F, and F cells, and mixed chimerism after BMT is sufficient to reverse the sickle phenotype by virtue of improved donor red cell survival compared to the ineffective erythropoiesis of SCD. The percentage of transferred globin necessary to cure SCD through a gene therapy approach and the relationship among ARC, amount of HbA and/or HbF, and measured red cell survival is currently unknown. Furthermore, RBC survival in patients with SCD who have successfully undergone HSCT has never been performed, as has the biotin methodology for individuals with SCT who are a critically important donor source for patients undergoing BMT.

Collection and biotinylation of RBCs in this study will allow the measurement and study of red cell survival in patients with and without SCD. The study of RBC survival and its relation to known influencers of red cell survival including ARC, % HbF, and F cell percentage will allow for the creation of a mathematical model that will help determine necessary amount of normal hemoglobin required to reverse the SCD phenotype. Such determination has the potential to influence current and future gene therapy protocols. Future questions include the ability to measure RBC lifespan in gene therapy patients, and the relationship of transferred globin (VCN) and percent engraftment of gene modified cells to the patient's RBC survival. As has been previously described (10), the reticulocyte fraction is a good proxy for RBC lifetime, and therefore gene therapy may be most efficacious in patients in which RBC survival is lowest (with highest reticulocyte count) as they would require lower amounts of normal hemoglobin production (lower levels of gene correction) to sufficiently reverse the SCD phenotype.

The population method will be used here to study RBC lifespan due to the safety, potential for a substantially shorter study period, and the possibility of being able to complex the labeling of the RBCs with other markers of interest.

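### Does Section 7.6 need to name an estimator and a fit window for mean potential lifespan (MPL)?

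*Combined protocol and SAP*

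**What the plan says.** Section 7.6 generates a survival curve for each participant. On the main summary it says "Mean potential RBC life span (MPL) will be determined by plotting the percentage of remaining biotinylated RBCs in circulation against time after transfusion". Median survival and mean cell age are also to be taken from these curves. The groups are then compared on this summary: "Average MPL among the groups studied will be examined descriptively using means and standard deviations". A further sentence reads "Correlation of mean RBC survival with known markers of red cell survival will be performed using Pearson Correlation". The section calls the study exploratory, does not generally expect significant differences, and uses the group differences to judge feasibility and guide larger studies.

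Section 7.7 assumes that "RBC lifetime is proportional to the inverse of the reticulocyte fraction" and will later build a model to "predict the percentage of necessary hemoglobin to reverse SCD from reticulocyte count and RBC half-life".

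On the length of the curve, Section 6.9 and Table 3 sample every group until the label falls to about 0.06%. Section 6.9 expects this to take 1 to 8 weeks in untransplanted SCD and 12 to 16 weeks in the other groups. Section 1.0 reports that a retrospective analysis suggests that "a 28-day window may be sufficient for accurate quantification of MPL". Section 3.0 gives "potential for a substantially shorter study period" as one reason for using a population label.

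**The concern.** Plotting is not an estimator. Section 7.6 does not say whether a line or another function is fitted, how points are weighted, or over what period. The synopsis names the primary endpoint only as red blood cell survival. Section 7.6 also correlates a mean survival that is not among its listed outputs, and Section 7.7 moves from lifetime to half-life without linking them.

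A reader who takes the 28-day remark together with sampling to 0.06% sees two possible fit windows. A population label declines in a straight line only when cells have similar lifespans. Section 1.0 says that survival of SCD cells varies with fetal hemoglobin content, and that transplanted patients can be stable mixed chimeras. In both cases the curve may bend, and the intercept of a fitted line then depends on the window. The group contrast, which is the purpose of the study, could move with a choice made after the data are seen.

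**Working it through.** The plan gives no worked MPL, power or effect size, so there is no figure to reproduce. The check asks what rule the text implies and how far other rules depart from it.

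**1. Implied estimator.** Section 1.0 says the label tags circulating cells irrespective of age. If all cells live L days and ages are spread evenly, the fraction remaining is R(t) = 1 − t/L. The line meets the time axis at L, which is the MPL. With lifespans X that vary, R(t) = E[max(X − t, 0)]/E[X].

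**2. Does the stated timeline fit?** Inputs from the protocol: lifespan 107 to 115 days (Section 1.0), about 32 days in SCD (synopsis), limit 0.06% (Section 6.9). Assumed: label at time zero L0 = 0.5 to 1.5%.
- Straight line, t = MPL × (1 − 0.06/L0): 107 × (1 − 0.06/0.5) = 94.2 days = 13.5 weeks; 115 × (1 − 0.06/1.5) = 110.4 days = 15.8 weeks.
- Exponential, t = mean × ln(L0/0.06): 107 × ln(0.5/0.06) = 226.9 days = 32.4 weeks; 115 × ln(1.5/0.06) = 370.2 days = 52.9 weeks.
- SCD at 32 days: straight 4.0 to 4.4 weeks, exponential 9.7 to 14.7.

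The plan's 12 to 16 weeks matches a near-linear decline. Its upper figure of 8 weeks for SCD lies between the two shapes, so some curvature there is plausible.

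**3. Effect of the window.** Noise-free curves with gamma lifespans, L0 = 1.0%, sampled on the plan's schedule with Week 1 as Day 0. MPL is the time-axis intercept of an unweighted line.

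| Curve | Lifespan CV (assumed) | To 0.06% | To day 28 |
|---|---|---|---|
| Healthy, mean 115 | 0 | 115.0 | 115.0 |
| Healthy, mean 115 | 0.2 | 117.7 | 115.0 |
| Healthy, mean 115 | 0.3 | 121.1 | 115.0 |
| SCD, mean 32 | 0 | 32.0 | 32.0 |
| SCD, mean 32 | 0.3 | 35.8 | 33.6 |
| SCD, mean 32 | 0.5 | 42.1 | 36.3 |
| SCD, mean 32 | 1.0 | 77.3 | 46.6 |

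**4. Mixed chimera.** Assume 90% of circulating cells at 115 days (CV 0.15), 10% at 32 days (CV 0.5) and L0 0.7 to 1.2%. The true mean is 1/(0.9/115 + 0.1/32) = 91.3 days. The line to 0.06% gives 111.7 to 114.7, the 28-day line 93.2 to 94.9, and twice the time to half the label (T50) 103.3. A healthy curve at CV 0.15 gives 115.7 to 117.6, 115.0 and 115.0. The gap to healthy is therefore about 3 to 4, 20 to 22 or 12 days. Ranges cover the starting label and both ways of counting weeks.

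**5. Would a 28-day rule be better?** With Week 1 as Day 0, the three groups other than untransplanted SCD are sampled on days 0, 7, 14, 21 and 35. A 28-day line there has four points and ends on day 21. With 2% proportional error (assumed) on a healthy curve, 95% of its values run from 94 to 153 days, against 114 to 117 for the full curve. With a larger assumed error (3 to 5% proportional plus 0.5% of baseline), noise per participant is 14 to 35% in healthy volunteers and 10 to 24% after transplant. With 3 and 6 participants (Section 5.1):
- lower end: √[(0.14 × 115)²/3 + (0.10 × 94)²/6] = √(86.4 + 14.7) ≈ 10 days;
- upper end: √[(0.35 × 115)²/3 + (0.24 × 94)²/6] = √(540 + 84.8) ≈ 25 days.

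The standard error of the 28-day group gap is thus about as large as the 20 to 22 day gap itself.

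**6. Undefined terms.** Median survival of a labelled population is naturally T50, so a half-life is already planned. T50/mean is 0.500 for a straight line, 0.522 for SCD at CV 0.5 and 0.566 for the 90:10 chimera. The healthy to SCD (CV 0.5) ratio is 57.5/16.71 = 3.44 by half-life and 115/32 = 3.59 by mean.

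**The case for a change.** The best case for a change is that survival is what this study measures, so its rule should be fixed before results are seen, and one sentence would do it. A sampling rule is not a fit rule. Even if the full curve is understood, the estimator is not named: on an exactly linear 115-day curve, an exponential fitted to all points down to 0.06% returns a mean of 49.3 days, and over 28 days 104.2. The full-curve line also overstates the mean where the decline bends, by 22 to 26% in the 90:10 chimera (111.7/91.3 to 114.7/91.3).

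What stands is that the rule is unwritten and that it matters for curved declines. The rest is weaker. An exponential contradicts the plan's own 12 to 16 weeks and would visibly miss a straight plot. The 28-day remark reports another analysis and is adopted nowhere. The shorter study period in Section 3.0 reads as an advantage over the cohort method, which Section 1.0 puts at about 150 days. No tested rule is best everywhere: the 28-day line is less biased in the chimera but much noisier, and the full line is precise but biased where the curve bends. The case therefore identifies an unstated choice without showing that a stated one is wrong or that another is better.

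**Conclusion.** No change follows. This is missing detail that analysts fill sensibly: a line through the full curve, with median survival beside it and each participant's curve available for inspection. For near-linear declines the window moves MPL little, 115.0 against 115.0 to 121.1 days for lifespan CVs up to 0.3. In SCD and mixed chimeras it can move MPL by several days to tens of days. Those sizes depend on lifespan CVs, mixture shares and starting label that the protocol does not give, so they show sensitivity and are not forecasts.

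The consequence is limited. Section 7.6 describes means and standard deviations in a pilot. No sample size or participant decision rests on MPL, and any summary can be recomputed from the curves. The loose terms in Sections 7.6 and 7.7 belong to descriptive correlations and to an exploratory model still to be developed. A second window or checks for two cell populations would be reasonable extras, but they are preferences and do not correct an error.
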